3.7.3 Other Efficacy Analyses

3.7.3.1. Quick Inventory of Depressive Symptomatology (QIDS-C16)

Since the HRSD does not measure hypersomnia, weight gain or problems with concentration or decision making, the Quick Inventory of Depressive Symptomatology (QIDS-C16), which meets the ACNP criteria is used for the additional MDD measurement (Rush et al., 2003). This is a clinician rated 16 item depressive assessment. Items 1-4 assess sleeping problem and the score is the highest of any 1 of the 4 items (max 3); items 6-9 assess weight problems and the score is the highest of any 1 of the 4 items (max 3); items 15-16 assess psychomotor problems and the score is the higher one (max 3); the remaining 6 items assess other MDD related functions and each item has one score (0-3). Thus, the total score for the nine MDD symptom domains (sleep, weight, psychomotor changes, depressed mood, decreased interest, fatigue, guilt, concentration, and suicidal ideation) range from 0 to 27. Higher score indicates more severe depression. At each time point of the baseline, end of acute treatment, and end of follow-up, mean and standard deviation of each item will be tabulated by treatment group (Tables 3.7.35a-c).

3.7.3.1.1. QIDS-C16 Score Overtime

The QIDS-C16 score at the baseline, end of each treatment block, and end of every four week follow-up time will be tested between the two treatment groups using

SAS PROC GLM at each visit. A mixed regression model will be used to test the main effects of treatment using SAS PROC MIXED. The model will include visit, treatment and treatment by visit interaction adjusted for the baseline. A means model will be assumed. An unstructured covariance model will be used in the analysis. If the model fails to converge a compound symmetry covariance matrix will be assumed. The restricted maximum likelihood (REML) method will be used to estimate the covariance parameters. If the treatment by visit interaction is not statistically significant then this term will be removed from the final model. The model is described in Section 3.7.1.2.5. The sample sizes, least-squares means, and standard deviations will be presented at each visit by treatment arm for each study visit (Tables 3.7.36a-c). The assumptions relating to the mixed-effects model will be reviewed by examining residual graphs. Scatter plots of residuals will be used to examine deviations from normality and to assess lack-of-fit. The least square means (LS-means) and their standard errors at each visit will be plotted by treatment groups (Figures 3.7.9a-c).

3.7.3.1.2. Depression Severity based on QIDS-C16 Score

QIDS-C16 score can be categorized into five depression severity groups, i.e. no depression (0-5), mild depression (6-10), moderate depression (11-15), severe depression (16-20), and very severe depression (21-27). The severity of the depression will be tested at end of the acute treatment, and end of the following-up using proportional odds model and SAS PROC LOGISTIC will be used to run the model and p-values related to the treatment effect will be presented. Further, the generalized linear mixed model will be applied to test the differences of the proportions of subjects' remission across all the time point. The link function will be cumulative logit. SAS PROC GLIMMIX will be used to analyze the data (Tables 3.7.37a-c).

3.7.3.2. Beck Hopelessness Scale (BHS)

As described in Section 2.5.3.8, the BHS is a 20-item self-report inventory developed by [name] that was designed to measure three major aspects of hopelessness: feelings about the future, loss of motivation, and expectations, consisting of 20 "yes/no" items with possible scores from 0 to 20 (Beck 1974). Higher score indicates more severe pessimism.

3.7.3.2.1. BHS Overtime

BHS at the baseline, end of each treatment block, and end of every four week follow-up time will be tested between the two treatment groups using SAS PROC GLM at each visit. A mixed regression model will be used to test the main effects of treatment using SAS PROC MIXED. The model will include visit, treatment and treatment by visit interaction adjusted for the baseline. A means model will be assumed. An unstructured covariance model will be used in the analysis. If the model fails to converge a compound symmetry covariance matrix will be assumed. The restricted maximum likelihood (REML) method will be used to estimate the covariance parameters. If the treatment by visit interaction is not statistically significant then this term will be removed from the final model. The model is described in Section 3.7.1.2.5. The sample sizes, least-squares means, and standard deviations will be presented at each visit by treatment arm for each study visit (Tables 3.7.38a-c). The assumptions relating to the mixed-effects model will be reviewed by examining residual graphs. Scatter plots of residuals will be used to examine deviations from normality and to assess lack-of-fit. The least square means (LS-means) and their standard errors at each visit will be plotted by treatment groups (Figures 3.7.10a-c).

3.7.3.2.2. Hopelessness Severity based on BHS

A total severity of hopelessness is calculated from summing the 20 items and guidelines for interpretation for scores are as follows: 0-3 = minimal hopelessness; 4-8 = mild hopelessness; 9-14 = moderate hopelessness; and 15-20 = severe hopelessness.. The severity of hopelessness will be tested at end of the acute treatment, and end of the following-up using proportional odds model and SAS PROC LOGISTIC will be used to run the model and p-values related to the treatment effect will be presented. Further, the generalized linear mixed model will be applied to test the differences of the proportions of subjects' remission across all the time point. The link function will be cumulative logit. SAS PROC GLIMMIX will be used to analyze the data (Tables 3.7.39a-c).

3.8 Safety Analyses

All safety analyses will be done for the safety population and reported in tabular forms. These analyses include adverse events/serious adverse events, vital signs, physical examinations, birth control/pregnancy test, safety trigger tests, and drug abuse and alcoholism tests.

3.8.1 Adverse Events

An adverse event is any symptom, sign, illness, or experience that develops or worsens in severity and/or frequency after the start of the study drug. Incidence of adverse events will be summarized for each treatment group by body system and MedDRA term. The number and percentage of subjects with each body system and MedDRA term will be presented for each treatment group. Pearson χ^2 test and/or Fisher Exact test were used to compare the frequency difference of AEs and SAEs between the treatment groups in System of Body (SOC) and Preferred Terms (PT) levels. Tables to summarize the incidence rates will be created for each of the following groups:

- Adverse events (Table 3.8.1)
- Adverse events by relationship to study treatment and device (Tables 3.8.2a-b)
- Adverse events by intensity (Table 3.8.3)
- Adverse events leading to premature discontinuation (Table 3.8.4)
- Adverse events presented in descending order of frequency by MedDRA term (no body systems shown) (Table 3.8.5)
- Serious adverse events (Table 3.8.6)

Adverse events that led to premature discontinuation from the study will be listed. Serious adverse events will also be listed. These listings will contain details about the adverse event such as intensity and relationship to study treatment. Other supportive data, such as the subject's age, will be given. All adverse events will be coded with MedDRA (updated version). The adverse events and severe adverse events will be listed by subject (Tables 3.8.7-8).

3.8.2. Vital Signs

Vital sign measurements include height (inches), weight (pounds), systolic and diastolic blood pressure (mmHg), pulse rate (beats/min), and oral temperature (in

Fahrenheit). Vital signs are measured at screening/baseline and the final treatment block. Vital signs mean changes from baseline to end of the treatment will be summarized. The summary will present data for the baseline visit and the mean change from baseline to the final evaluation. For each visit, the sample size, mean, SD, median, minimum, and maximum values for each treatment will be presented for each parameter (Table 3.8.9), and tested using SAS PROC TTEST. If vital signs are not normally distributed the non-parametric method will be applied using SAS PROC NPAR1WAY.

3.8.3. Physical Examination

Physical examinations will be performed at screening/baseline and the final treatment block. Each body system will be categorized as abnormal, normal, or not done. Abnormal physical examination will be recorded in text. Physical examination changes from baseline to will be categorized as improved, no change, or worsened for each body system. The number and percentage of subjects in each category of change will be given at each visit for each treatment group and body system (Table 3.8.10). SAS PROC GENMOD will be used to test these physical parameters adjusted for the baselines.

3.8.4. Birth Control and Pregnancy Test

Birth control and pregnancy test data will be collected within 7 days prior to randomization and every 4 weeks thereafter throughout the study. The number and percentage of subjects for each category of method of birth control use and pregnancy test results (N/A (male), Not done, Negative, and Positive) will be presented at each test for each treatment groups and all subjects Table 3.8.11 and Table 3.8.12 respectively.

3.8.5. Trigger Tests

3.8.5.1. Columbia – Suicide Severity Rating Scale (C-SSRS)

The C-SSRS is a measure of suicidal ideation and behavior. The primary outcomes of the measurement are suicidal ideation (1-5 items), suicidal behavior (6-10 items), and self-injurious behavior without suicidal intent; and the secondary outcomes are number of suicidal behaviors (total number of each type of suicidal behavior, i.e.

suicide attempts, aborted attempts, and interrupted attempts) and lethality rating (rated 1-5) for suicidal behavior, and severity rating (rated 0-5) and intensity (scored 0-25) for suicidal ideation. The baseline scores are compared with those of past six month, while the follow-up scores are compared with those from last visit.

The number and percentage of subjects for each category of suicidal ideation, suicidal behavior, completed suicide, as well as self-injurious behavior without suicidal intent, will be presented at each measurement by the treatment groups and all subjects (Table 3.8.13). The difference of suicidal ideation, suicidal behavior, suicidal ideation or behavior, completed suicide and self-injurious behavior without suicidal intent between the treatment groups will be tested at each measurement time point using Fisher exact test in SAS PROC FREQ when events are rare. Further, the generalized linear mixed model will be applied to test the differences of the proportions across all the time point. SAS PROC GLIMMIX will be used to analyze the data. For the generalized linear mixed models will include visit, treatment and the visit and treatment interaction adjusted for the baseline measurement. then, Intensity of ideation will also be analyzed based on the most severe ideation, frequency, duration, controllability, deterrents, and reasons for ideation which are tabulated in Table 3.8.14a. The difference of these intensity items will be tested at each measurement time point using Fisher exact test. The intensity scores for each category and the total scores of all five categories at the baseline, end of each treatment block, and end of every four week follow-up time will be tested between the two treatment groups using SAS PROC GLM at each visit. A mixed regression model will be used to test the main effects of treatment using SAS PROC MIXED. The model will include visit, treatment and treatment by visit interaction adjusted for the baseline as shown Table 3.8.14b.

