2.5.4. Safety Assessment and Triggers

2.5.4.1. Columbia – Suicide Severity Rating Scale (C-SSRS)

Suicide is a rare event. As such, suicide rates cannot be used as an outcome measure for an rTMS study. Similarly, the study is of too short a duration to expect to find a significant difference in numbers or lethality of suicide attempts between treatment and placebo (sham rTMS) groups. Nonetheless, there are two areas that can be expected to change with successful rTMS treatment: preoccupation with suicidal ideations or plans. Because this study uses both a lead in period prior to treatment and a sham rTMS treatment group, we are able to compare the rate of parasuicidal behavior in these patients, who are at more serious risk of a suicide completion. One of the newer methods of monitoring patients at risk for suicide is the C-SSRS. The C-SSRS assesses suicidal ideation as well suicidal behavior over a specified time period and is frequently employed by the Food and Drug Administration in research to determine if suicidality is an adverse effect. The form is collected at multiple time points in during the course of the study. Initially, it is collected at baseline to serve as a screener for persons reporting suicidal ideation or behaviors in the past six months. It is also completed weekly during acute treatment and then monthly during the follow-up phase to monitor for the presence of suicidal ideation or behaviors. The sensitivity of this instrument will allow us to identify even “minor” suicide “gestures” as well as more serious attempts.

2.5.4.2. *State-Trait Anger Expression Inventory -2 (STAXI-2)*

The STAXI-2 is a 57-item self-report measure of the experience, expression, and control of anger. The measure consists of six scale, five subscales, and Anger Expression Index which provides a measure of total anger expression. The STAXI-2 is frequently included in risk assessments for violence and used as such in the current protocol.

2.5.4.3. *Adverse events (AEs)*

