2.6 Sample Size Consideration

The primary hypothesis of the study is that in VA patients with TRMD, rTMS will result in a greater remission rate at the end of acute treatment than sham rTMS. The primary outcome measure in this study is success or failure to achieve remission from depression as defined by a score on the Hamilton Rating Scale for Depression (HRSD24) of 10 or less. The primary analysis will be done as an "intent-to-treat" analysis, i.e. patients will be analyzed in the groups to which they were randomized and drop-outs will be considered treatment failures. The primary hypothesis will be addressed using a logistic regression model with PTSD diagnosis, history of substance abuse, and site as covariates. Based on review of the studies reported in the Introduction Section, the Planning Committee felt that a 10% difference between treatments would be of clinical relevance given the severity of the illness. With a sample size of 180 per group, the proposed study will have a power of 81% to detect an absolute difference between groups of 10% in the percentage of those participants who remit (6% sham and 16% rTMS). Thus, a total of 360 patients are required. This goal of 360 patients, larger than any previous study, also provides a measure of protection should some assumptions be wrong.

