3.1.2 Analysis Conventions

This section details general policies to be used for the statistical analyses. Departures from these general policies may be given in the specific detailed sections of this statistical analysis plan. When this situation occurs, the rules set forth in the specific section take precedence over the general policies. The following policies will be applied to all data presentations and analyses.

- All statistical tests will use a significance level of $\alpha = 0.05$. Two-tailed tests will be performed for all analyses that use statistical testing.
- All p-values will be rounded to 3 decimal places. All p-values that round to 0.000 will be presented as '<0.001' and p-values that round to 1.000 will be presented as '>0.999'. Any p-value $\leq \alpha$ will be considered statistically significant.
- Summary statistics will consist of the number and percentage of responses in each category for discrete variables, and the mean, median, standard deviation (SD), minimum, and maximum for continuous variables.
- All mean and median values will be formatted to one more decimal place than the measured value. Standard deviation values will be formatted to two more decimal places than the measured value.
- All percentages will be rounded to one decimal place. The number and percentage of responses will be presented in the form XX (XX.X), where the

- percentage is in the parentheses. The decimal of the percentage may be dropped due to space constraints when creating a table.
- For a continuous variable, if it is normally distributed or approximately normally distributed, Student t test and/or the general linear regression will be performed to test the group difference as proposed in the analysis plan, otherwise, Wilcoxon test and/or a quantile regression will be used as an alternative analysis method; for a categorical variable, Pearson χ^2 test and/or a corresponding generalized linear regression will be performed to test the group difference.
 - All listings will be sorted for presentation in order of treatment group, site number, subject number, and date of procedure or event.
 - All analysis and summary tables will have the population sample size for each treatment group in the column heading.
 - Calculating change from baseline to a visit will be done as follows: change = visit –baseline.

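### The C-SSRS analysis tests suicidal behaviour and self-injury visit by visit and defines no per-patient comparison over the study

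*SAP*

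**What the plan says.** Section 2.5.4.1 gives the purpose of the C-SSRS. With a sham arm and a lead-in period, "we are able to compare the rate of parasuicidal behavior in these patients", and the instrument is expected to pick up even minor gestures. The same section calls suicide rare and says the trial is too short to expect a significant difference in the number or lethality of attempts.

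Section 3.8.5.1 sets the analysis:

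- **Counts.** The number and percentage in each category "will be presented at each measurement by the treatment groups and all subjects (Table 3.8.13").
- **Tests.** Differences between arms "will be tested at each measurement time point using Fisher exact test in SAS PROC FREQ when events are rare".
- **Model across visits.** A generalized linear mixed model (PROC GLIMMIX) with visit, treatment, their interaction and the baseline value.
- **Look-back.** "The baseline scores are compared with those of past six month, while the follow-up scores are compared with those from last visit".

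The section names the total number of each type of suicidal behaviour as a secondary C-SSRS outcome and then gives it no analysis. The table list titles Table 3.8.13 as a number of patients over the treatment period, whereas the text describes a count at each measurement.

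**The concern.** The stated aim is a comparison of how often parasuicidal behaviour occurs in the two arms. For a rare event, that calls for a count of patients affected over a period. Section 3.8.5.1 instead divides the few events among many visits and tests each visit alone. Printed visit counts cannot be added up afterwards to give a patient count, because the same patient may appear at more than one visit.

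The mixed model is the only C-SSRS comparison of these categories across time, and its interaction term needs events in both arms at each visit. A run of non-significant visit tests and an unstable model could then be reported as no difference in suicidal behaviour, on a named safety outcome, when the analysis had little chance of showing one.

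**Working it through.** **Inputs**

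- Arm size: 180, from Section 2.6 ("With a sample size of 180 per group, the proposed study will have a power of 81"%), taken as the safety denominator. This assumes every randomised patient had at least one session.
- Test level, Section 3.1.2: "All statistical tests will use a significance level of" 0.05, and "Two-tailed tests will be performed for all analyses that use statistical testing".
- Visits: the schedule in Appendix 5.2 has up to 6 C-SSRS measurements in acute treatment, 3 in taper and 5 to 6 in follow-up, so 14 to 15. I use 15, and 6 for the case where all events fall in acute treatment.
- Event rates: the SAP gives none. All rates below are assumptions.

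**The plan's own figure.** The SAP states power only for remission, "in the percentage of those participants who remit (6% sham and 16% rTMS"). At 180 per arm the two-proportion formula gives 86.1% without and 82.0% with continuity correction; the exact power of Fisher's test is 83.3%. The stated 81% is therefore reproduced to within 2 points with the correction, and 180 per arm is a sound base. No figure is stated for the C-SSRS.

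**What one visit needs.** Two-sided Fisher test, 180 per arm:

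| Events | p |
|---|---|
| 0 v 5 | 0.061 |
| 0 v 6 | 0.030 |
| 1 v 8 | 0.037 |
| 2 v 10 | 0.035 |

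**Chance of seeing a rise.** Let a proportion p of an arm ever be affected, with one event each spread evenly over K visits, so the risk at one visit is p/K. At 2% v 7% and K = 15, the expected events per visit are 180 × 0.02/15 = 0.24 and 180 × 0.07/15 = 0.84, far from 0 v 6. Summing the binomial probabilities over all outcomes with Fisher p ≤ 0.05 in the direction of a rise gives the power v at one visit. The chance that any visit is significant is 1 − (1 − v)^K, treating visits as independent:

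- K = 15: v = 0.000177, so 1 − (1 − 0.000177)^15 = 0.27%.
- K = 6: v = 0.01128, so 1 − (1 − 0.01128)^6 = 6.6%.

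| Ever affected | Any of 15 visits | Any of 6 visits | One per-patient Fisher test |
|---|---|---|---|
| 1% v 3% | <0.01% | 0.1% | 14% |
| 2% v 6% | 0.1% | 3.3% | 39% |
| 2% v 7% | 0.3% | 6.6% | 55% |
| 3% v 10% | 1.5% | 21% | 73% |
| 3% v 12% | 3.6% | 37% | 89% |

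Allocating simulated events to visits at random, without the independence approximation, gives the same picture (2% v 7%: 0.3% and 6.6%).

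**The mixed model.** At a visit with a events of 180 on sham and b of 180 on rTMS, the log odds ratio is log[b/(180 − b)] − log[a/(180 − a)], which is not finite if a or b is 0. At 2% v 7% and K = 15, the chance of no event at a visit is (1 − 0.02/15)^180 = 0.786 in one arm and (1 − 0.07/15)^180 = 0.431 in the other. At least one arm is empty with probability 0.786 + 0.431 − 0.786 × 0.431 = 0.878 (0.60 at K = 6). Most interaction terms would have no finite estimate.

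For HRSD, Section 3.7.1.2.5 drops a non-significant interaction and names a fallback covariance, and the convergence rule in Section 3.7 is limited to efficacy analyses. Section 3.8.5.1 has no counterpart to either.

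**The case against.** **Suicidal events are compared cumulatively elsewhere.** The AE definition in Section 3.8.1 is wide enough for new or worse ideation, self-injury and attempts. Tables 3.8.1 and 3.8.6 give cumulative AE and SAE incidence, with chi-square or Fisher tests at preferred-term level. This stands. A reader might infer that a rise in suicidal events cannot be seen at all; the SAP does not support that. What has no cumulative comparison is events recorded only on the C-SSRS, such as aborted or interrupted attempts and minor gestures not reported as AEs.

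**Table 3.8.13 may already be a patient count.** Its title can be read that way, and the shells are a separate attachment. But the text of Section 3.8.5.1 says otherwise and defines no rule for a patient total. The two need reconciling.

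**The SAP disclaims power for attempts.** It does, for their number and lethality. The same section still promises a comparison of parasuicidal behaviour, and where significance is not expected, an estimate with its interval matters more.

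**The look-back windows.** A reader might think that a six-month baseline window against one to four weeks later helps to hide a rise. It does not: post-baseline windows follow the same schedule in both arms, and the six-month window applies only to the baseline covariate.

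**The arithmetic is favourable to the point.** One event per patient spread evenly is an assumption, and it does not fit ideation, which can recur across visits. Nor does every visit test fail whatever the excess: at 3% v 12% over 6 visits the chance of a significant visit is 37%. The mixed model was not fitted; the weakness shown is that its empty cells are likely and no rule covers them.

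**Conclusion.** The point holds for behaviour and self-injury captured on the C-SSRS alone. Section 3.8.5.1 does not deliver the comparison that Section 2.5.4.1 announces: there is no per-patient endpoint, the visit tests have almost no power for rare events, and the model across visits has no rule for the sparse cells it will probably meet. At an assumed 2% v 7% ever affected, the chance of any significant visit is about 0.3% (15 visits) or 7% (6 visits), against 55% for one per-patient test. These figures rest on 180 per arm, one event per affected patient, an even spread and rates the SAP does not give. The contrast keeps its direction at every rate tried, but narrows when events are more common or fall in fewer visits.

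The change should be made, but it does not make the trial well powered for small rises: the per-patient test has 14% power at 1% v 3% and 39% at 2% v 6%.

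**What to change.** In Section 3.8.5.1 and Table 3.8.13:

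1. For each C-SSRS category, add the number of patients with any event after the first session. For ideation, count ideation new or worse than baseline. Report acute plus taper, and the whole study.
2. Compare arms with Fisher's exact test and an exact 95% CI for the risk difference. Make this the main C-SSRS comparison, and always report the interval, given the modest power.
3. Keep the visit-by-visit counts as description.
4. For rare categories, omit the visit-by-treatment term from the GLIMMIX model.
5. Make the table title and the text agree on what is counted and over which period.

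Events per person-time could be added but are not essential. The cost is some SAP wording and one derived flag per category from data already collected. The downside is less weight on the per-visit p-values.
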